### **12.1.3 Discontinuation of Study Agent**

If the patient discontinues pembrolizumab (MK-3475), patients should be followed for survival per the study calendar ([Section 5.0](#)).

## **12.2 Follow-up for patients who stop protocol therapy**

### **12.2.1 Withdrawal of consent**

Patients who withdraw consent should not be followed anymore and should not be contacted for any study related inquiries.

### **12.2.2 Stopping study treatment due to toxicity**

If the patient discontinues study treatment due to toxicity they will be followed for survival per the study calendar ([Section 5.0](#)).

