- \*\* Physical examination, adverse event assessments, labs and scans are required  $\leq 12$  weeks after the end of treatment; thereafter, every 6 months until disease progression for a maximum of 5 years following registration or more frequently as clinically indicated. See also [Section 12.0](#). At time of progression, withdrawal or removal, only survival information should be collected every 6 months for 5 years after registration.
- \*\*\* Radiation therapy will be administered to 1 cancer deposit concurrent with the first dose or started within the first cycle of pembrolizumab (MK-3475) administration. Eligibility must have been documented prior to administration of radiation.
- † Only required if there is evidence or suspected brain mets
- # All sites of known disease as clinically indicated.
- 1 To be completed after registration and prior to treatment (See Appendix I). This questionnaire is included on all Alliance trials in order to further study the relationship between these assessments and overall survival in a meta-analysis setting.
- 2 For women of childbearing potential (see [Section 3.2](#)). Must be done  $\leq 7$  days prior to registration.
- 3 Baseline scans can include either: 1) a CT, spiral CT, or MRI or 2) an FDG-PET scan and diagnostic CT performed with both IV and oral contrast, and the CT acquired with 5 mm or less slice thickness. Supporting documentation is to be submitted, per [Section 6.1](#). Response assessment should include assessment of all sites of disease and use the same imaging method as was used at baseline.
- A After Cycle 3 (prior to cycle 4) then every 9 weeks, (prior to the start of cycles 4, 7, 10, 13, 15, etc.).

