## 12.0 END OF TREATMENT/INTERVENTION

### 12.1 Duration of Treatment

#### 12.1.1 CR, PR, or SD

Patients who are in CR, PR or SD will continue on therapy for a total of two years of treatment. After treatment is discontinued, patients will be followed per the study calendar in [section 5.0](#).

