#### 12.1.2 Disease Progression

Remove from protocol therapy any patient with confirmed disease progression. Document details, including tumor measurements, on data forms. Patients who are clinically well may

continue on therapy following RECIST progression with new lesions or increase in target lesions if the increase in disease burden does not meet the definition of iCPD by immune response criteria [24] outlined in [section 11.5](#).

After removal for disease progression, patients should be followed for survival per the study calendar ([Section 5.0](#)).

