### **Follow-up for ineligible patients who discontinue protocol treatment**

For patients who are deemed ineligible after registering to the trial, who start treatment, but then discontinue study treatment, the same data submission requirements are to be followed as for those patients who are eligible and who discontinue study treatment.

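### The protocol does not settle whether patients who stop pembrolizumab without progression keep having the tumor assessments that primary PFS needs

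*Combined protocol and SAP*

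**What the plan says.** Section 12.2.2 reads "If the patient discontinues study treatment due to toxicity they will be followed for survival per the study calendar", and Section 12.1.3 reads "If the patient discontinues pembrolizumab (MK-3475), patients should be followed for survival per the study calendar". Section 12.1.2 uses the same phrase once disease has progressed: "After removal for disease progression, patients should be followed for survival per the study calendar". For patients in CR, PR or SD, Section 12.1.1 makes no mention of survival: "After treatment is discontinued, patients will be followed per the study calendar".

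The calendar in Section 5.0 marks tumor measurement and CT/MRI in its post-treatment column. The first sentence of footnote ** asks for scans no later than 12 weeks after treatment ends and "thereafter, every 6 months until disease progression for a maximum of 5 years following registration". The last sentence of the same footnote says "At time of progression, withdrawal or removal, only survival information should be collected every 6 months for 5 years after registration".

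Other places bear on the question:
- Section 12.3 asks for progression data even from registered patients who were never treated. For ineligible patients who start and then stop, it says "the same data submission requirements are to be followed as for those patients who are eligible and who discontinue study treatment", so they inherit whichever rule applies.
- Section 12.4 covers therapy stopped because the protocol harms the patient or the patient wishes to stop. It asks for follow-up of the protocol's endpoints.
- Section 13.2.1 measures PFS from randomization to progression or death and censors patients without an event at their last progression assessment. It does not close PFS follow-up when treatment stops for toxicity.

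**The concern.** A site comparing the neighbouring paragraphs of Section 12 can fairly conclude that a patient who stops for toxicity moves to survival follow-up, as after progression. That patient would then supply less endpoint data than one who was randomized and never treated.

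On that reading, a progression after the stop is never seen. The patient is censored at the last on-treatment scan or becomes a PFS event only at death. This touches primary PFS and the 75-event trigger (13.2.2, 13.3.3). It also touches three secondary endpoints in 13.4.1: PFS across all RECIST lesions, PFS at 6 months, and local control of the irradiated tumor.

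Footnote ** adds a smaller difficulty. If its *withdrawal* includes withdrawal of consent, continued collection of survival data conflicts with Section 12.2.1: "Patients who withdraw consent should not be followed anymore and should not be contacted for any study related inquiries".

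**Working it through.** **1. The text.** Everything turns on *removal* in the last sentence of footnote **. Section 12.1.2 uses the word for leaving protocol therapy at progression; Section 13.2.1 uses it for leaving the study. If it covers a toxicity stop, the footnote's last sentence agrees with 12.1.3 and 12.2.2, and 12.1.1, 12.4 and the footnote's first sentence are out of line. If it does not, the footnote is coherent and requires scans, and 12.1.3 and 12.2.2 are out of line. Neither reading reconciles every place.

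**2. The plan's design figures.** Inputs from 13.2.2: hazard ratio 9/13.5 = 0.667, one-sided alpha 0.20, 75 events, cut-offs 1.013 at 38 events and 0.837 at 75.
- Single-look power (Schoenfeld): Φ(|ln 0.667|·√75/2 − 0.842) = Φ(1.756 − 0.842) = 0.820.
- With the futility look, the boundaries are z₁ = −ln(1.013)·√38/2 = −0.040 and z₂ = −ln(0.837)·√75/2 = 0.770, with correlation √(38/75). The bivariate normal gives power 0.802 and alpha 0.199, against 0.80 and 0.20 stated.
- Expected events at month t, with 1.5 patients per arm per month for 32 months (13.3.2), are the sum over arms of 1.5·[32 − (e^(−λ(t−32)) − e^(−λt))/λ], λ = ln 2/median. At t = 41 this is 39.1 + 33.1 = 72.2; 75 is reached at about month 43, against about 41 stated. Events are therefore compared at month 43.

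**3. Simulation of the two readings.** 4,000 trials per scenario, both rules applied to the same simulated patients.
- From the documents: 96 patients 1:1 at 3 per month, exponential PFS with medians 9 and 13.5 months, 9-week scans on treatment, 24-month maximum treatment, 60-month follow-up.
- Assumed: 10, 20 or 35% assigned a stop, uniform over months 1–9 (7, 15 or 26% actually stop before progression); stopping equal by arm and unrelated to prognosis; 15% of first events are deaths; median post-progression survival 12 months.
- Progression is recorded at the next scan, or at death if earlier. The interim look and stratification are ignored.

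| Calendar scans → survival-only | 10% | 20% | 35% |
|---|---|---|---|
| Events at month 43 | 73.1 → 71.5 | 72.9 → 69.6 | 72.7 → 67.1 |
| Delay of 75th event (months) | 1.4 | 2.9 | 5.2 |
| Hazard ratio at 75th event | 0.669 → 0.675 | 0.663 → 0.679 | 0.668 → 0.700 |
| P(HR ≤ 0.837) | 0.832 → 0.822 | 0.832 → 0.809 | 0.833 → 0.774 |

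Standard errors of the paired differences are 0.02–0.04 event, 0.02–0.04 month and 0.004–0.006 in probability. A separately programmed run of 1,500 trials gave losses of 1.7, 3.5 and 6.2 events and delays of 1.4, 3.1 and 5.5 months.

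**4. Sensitivity.** With 20% stopping and median post-progression survival of 6–18 months, the loss is 1.7–4.2 events and the delay 1.4–4.0 months. Under the null (20 and 35% stopping) the hazard ratio stays near 1.00 and P(HR ≤ 0.837) changes by −0.004 and −0.005 (SE 0.005–0.006). If the lost events were never recovered, single-look power would fall from 0.820 to 0.815, 0.809 and 0.80.

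**5. PFS at 6 months.** Twelve weeks is 2.76 months, so a stop at month s gives calendar scans at s + 2.76 and s + 8.76. On-treatment scans fall at 2.07, 4.14 and 6.21. Count a scan in months 5–7.5 as a month-6 assessment.
- Calendar scans miss stops in months 1–2.24 and 4.74–6.21: 1.24 + 1.47 = 2.71 of the 8-month range.
- Survival-only misses stops in months 1–6.21: 5.21 of 8.
- The ratio is 0.52. In simulation, 2.4, 4.8 and 8.4 of 96 patients had neither an event by month 6 nor a scan in the window under calendar scans, against 5.1, 10.1 and 17.9 under survival-only.

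**The case against.** The strongest reply is that the protocol, read as a whole, already asks for progression follow-up. Sections 12.1.3 and 12.2.2 both defer to the calendar, and the first sentence of footnote ** applies after the end of treatment whatever the reason. Section 12.4 fits a toxicity stop. Section 6.1.3 requires a radiology report at progression with no on-treatment limit. Section 11.4.5 asks that objective progression be documented even after treatment has stopped for symptomatic deterioration. Section 9.2 provides for adverse events in a clinical follow-up phase. The Data Submission Schedule named in 6.1.1 is not in these documents and may settle what sites submit.

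Much of this stands: continued assessment is the better-supported reading. It does not remove the conflict, because the two sections a site would consult after a toxicity stop use the post-progression wording, and the footnote's last sentence can be read to support them.

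A reader might infer that 12.1.3 and 12.2.2 flatly contradict the calendar. The documents do not support that, since the same footnote also contains a survival-only rule. A reader might also infer that calendar scans would restore every month-6 assessment. They would not: a 12-week scan followed by 6-monthly scans leaves about half of the gap.

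**Conclusion.** The point holds as an unresolved ambiguity in follow-up, not as a proven contradiction or a proven loss of data. If sites read the text as survival-only, and 10–20% of patients are assigned an early stop, the trial records about 1.6–3.3 fewer PFS events at month 43, reaches its 75th event 1.4–2.9 months later, and has a probability of meeting the 0.837 cut-off lower by about 0.01–0.02. At 35% the delay is 5.2 months and the probability falls by 0.06.

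These sizes rest on assumed stopping rates, stopping equal in both arms and unrelated to prognosis, and an assumed post-progression survival. The main effect is delay, with slight dilution of a true benefit. Unequal or prognosis-related stopping could bias the hazard ratio, but nothing in the documents establishes that it occurs or in which direction. The effect is modest; the case for acting is that primary-endpoint ascertainment should not depend on how each site reads one word.

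**What to change.** Reconcile three places.
- In 12.1.3 and 12.2.2, state that patients who stop treatment without RECIST progression keep the tumor assessments already scheduled in Section 5.0 until progression, as 13.2.1 needs. Survival-only follow-up begins once progression is recorded and treatment has ended.
- In footnote **, define or delete *removal*, and align *withdrawal* with 12.2.1.
- Check the Data Submission Schedule against the result.

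Section 13.2.1 needs no edit. The requirement in 13.4.1 that a 6-month success remain on study is also undefined after a treatment stop; this change does not resolve it.

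The cost is wording, plus continued scan-data collection in patients off treatment. The assessments are already in the calendar, although a site that has followed the survival-only reading would see them as added work. The amendment notice says accrual is permanently closed, so the gain is confined to patients still in follow-up or whose scans can be retrieved.

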## **12.3 Managing ineligible patients and registered patients who never receive protocol intervention**

### **Definition of ineligible patient**

A study participant who is registered to the trial but does not meet all of the eligibility criteria is deemed to be ineligible.

### **Follow-up for ineligible patients who continue with protocol treatment**

Patients who are deemed ineligible after registering may continue protocol treatment, provided the treating physician, study chair, and executive officer agree there are no safety concerns if the patient continues protocol treatment. All scans, tests, and data submission are to continue as if the patient were eligible. Notification of the local IRB may be necessary per local IRB policies.

### **Follow-up for ineligible patients who discontinue protocol treatment**

For patients who are deemed ineligible after registering to the trial, who start treatment, but then discontinue study treatment, the same data submission requirements are to be followed as for those patients who are eligible and who discontinue study treatment.

### **Follow-up for patients who are registered, but who never start study treatment**

For all study participants who are registered to the trial but who never receive study intervention (regardless of eligibility), the follow-up requirements are specified below.

Randomized phase II and phase III: Baseline, off treatment, and post-treatment follow up (i.e., relapse, progression, and survival) data submission required. See the Data Submission Schedule accompanying the All Forms Packet.

## **12.4 Extraordinary Medical Circumstances**

If, at any time the constraints of this protocol are detrimental to the patient's health and/or the patient no longer wishes to continue protocol therapy, protocol therapy shall be discontinued. In this event:

Document the reason(s) for discontinuation of therapy on data forms.

Follow the patient for protocol endpoints as required by the Study Calendar.

### 13.0 STATISTICAL CONSIDERATIONS

#### 13.1 Study Design

The study population in this randomized phase II trial are patients with advanced Merkel cell carcinoma. The trial is designed to compare Progression Free Survival (PFS) in patients that receive SBRT + pembrolizumab (MK-3475) compared to pembrolizumab (MK-3475) alone in non-radiated lesion(s). This trial implements a group sequential design with one interim analysis for futility. East v6 was utilized to create the statistical design described below.

#### 13.2 Statistical Design and Analysis for the Primary Endpoint

##### 13.2.1 Primary Endpoint:

We are comparing the Progression Free Survival (PFS) in non-radiated lesion(s) of patients receiving either (a) SBRT + pembrolizumab (MK-3475) compared to (b) pembrolizumab (MK-3475) alone in patients with advanced Merkel cell carcinoma. For each patient, during screening, one lesion will be identified as the one to be potentially radiated (if randomized to the arm with SBRT). Then up to 5 additional lesions will be identified that are followed for PFS. For patients in both arms, the lesion identified to be radiated (pre-randomization) will be followed separately (i.e. it will not be a target lesion). If this lesion changes in a way that leads to a change in the patient's treatment (e.g. adding a non-protocol treatment or removal of the patient from the study), then the patient's PFS data would be considered censored at the time of the change in their treatment.

A patient is considered an event for this endpoint at the time of first evidence of disease progression or death (without evidence of progression) and their PFS time is defined as the time from randomization to either disease progression or death (without progression). For patients that are not considered an event for this endpoint, the PFS time will be censored at their last evaluation for progression. All randomized patients meeting the eligibility criteria who received any quantity of their randomized care and did not have a major treatment violation will be part of the analysis group for the primary endpoint.

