#### 3.2.2 Measurable disease and/or non-measurable disease as defined in Section 11.0.

Have measurable disease based on RECIST 1.1 including at least two cancerous deposits. At least one deposit must be RECIST measurable while at least *one deposit* must meet criteria for SBRT (See [Section 7.1](#)). Non-irradiated tumor will be identified prior to randomization on the protocol.

\_\_\_ **3.2.3 Patients must have advanced or metastatic MCC defined as evidence of distant metastasis(es) on imaging.**

- Patients with locoregionally confined disease are not eligible.

\_\_\_ **3.2.4 Prior Treatment**

- No prior immunotherapy for advanced/metastatic MCC
- Patients with known or suspected CNS metastases, untreated CNS metastases, or with the CNS as the only site of disease are excluded. However, subjects with controlled brain metastases will be allowed to enroll. Controlled brain metastases are defined as no radiographic progression for at least 4 weeks following radiation and/or surgical treatment (or 4 weeks of observation if no intervention is clinically indicated), and off of steroids for at least 2 weeks, and no new or progressive neurological signs and symptoms
- Patients having received palliative radiotherapy for extracranial metastasis(es) are eligible as long as there are 2 cancerous deposits that have not received prior RT and they meet the following criteria.
  - o No prior radiation therapy (>5 Gy) to the metastasis intended to be treated with SBRT

\_\_\_ **3.2.5 No History of the following:**

- Autoimmunity requiring systemic immunosuppression within 2 years
- Patients known to be HIV positive are eligible if they meet the following:
  - CD4 counts  $\geq 350 \text{ mm}^3$
  - Serum HIV viral load of  $<25,000 \text{ IU/ml}$ .

\_\_\_ **3.2.6 No other active malignancy that the investigator determines would interfere with the treatment and safety analysis.**

\_\_\_ **3.2.7 Not pregnant and not nursing**, because this study involves an investigational agent whose genotoxic, mutagenic and teratogenic effects on the developing fetus and newborn are unknown.

Therefore, for women of childbearing potential only, a negative (if your test schedule specifically indicates a urine or serum pregnancy test, add that information at this point) pregnancy test done  $\leq 28$  days prior to registration is required.

\_\_\_ **3.2.8 Age  $\geq 18$  years**

\_\_\_ **3.2.9 ECOG Performance Status 0-2**

\_\_\_ **3.2.10 Required Initial Laboratory Values:**

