### **7.0 TREATMENT PLAN/INTERVENTION**

Protocol treatment is to begin  $\leq 21$  days of registration.

For questions regarding treatment, please see the study contacts page.

It is acceptable for individual pembrolizumab (MK-3475) to be delivered  $\leq$  a 72-hour (business day) window before and after the protocol-defined date for Day 1 of a new cycle. For example, if the treatment due date is a Friday, the window for treatment includes the preceding Tuesday through the following Monday. In addition, patients are permitted to have a new cycle of pembrolizumab (MK-3475) delayed up to 7 days for major life events (e.g., serious illness in a family member, major holiday, vacation that cannot be rescheduled) without this being considered a protocol violation. Documentation to justify this delay should be provided.

Pembrolizumab (MK-3475) is administered on an outpatient basis. Infusion timing should be as close to 30 minutes as possible; however, a window of -5 minutes and +10 minutes is permitted (*i.e.*, infusion time is 25-40 minutes). Please refer to Section 10.2 for pembrolizumab (MK-3475) compatible infusion set materials, including in-line filter.

Protocol therapy will include pembrolizumab (MK-3475) in both arms (Arms 1 & 2) and radiation (SBRT) in one arm (Arm 2). Radiation will be administered concurrent with the first dose or started

within the first cycle of pembrolizumab (MK-3475). The radiated lesion will be identified prior to randomization and that this lesion will be excluded from the primary endpoint (PFS) calculation. pembrolizumab (MK-3475) treatment will be administered once every 21 days (1 cycle). Treatment will continue until disease progression or unacceptable adverse event for a maximum period of two years.

Agent	Dose	Route	Day	ReRx
pembrolizumab (MK-3475)	200 mg	IV	Day 1	every 3 weeks

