**Table 1.9 Normal Structure Constraints and Compliance Criteria**

Serial Organ	Dosimetric Priority	Volume	Volume Dose (Gy)
Spinal Cord	1	<0.03 cc	22.5

		<1.2 cc	13
Ipsilateral Brachial Plexus	1	< 0.03 cc	26
		<3 cc	22
Cauda Equina	1	<0.03 cc	22.5
		<5 cc	21.9
Sacral Plexus	1	<0.03 cc	24
		<5 cc	22.5
Trachea and Ipsilateral Bronchus (Non-adjacent wall)	3	<0.03 cc	30
		<5cc	25.8
Esophagus (Non-adjacent wall)	1	<0.03 cc	27
		<5cc	17.7
Heart/Pericardium	1	<0.03cc	30
		<15 cc	24
Great vessels (Non-adjacent wall)	3	<0.03cc	45
		<10 cc	39
Skin (non-tumor involved)	1	<0.03cc	33
		<10cc	31
Stomach	1	<0.03cc	30
		<10cc	22.5
Duodenum*	1	<0.03cc	24
		<10cc	15
Jejunum/ileum*	1	<0.03cc	27
		<30cc	17.4

Bowel*	1	<0.03 cc	34.5
		<20cc	24
Rectum*	3	<0.03 cc	49.5
		<3.5 cc	45
		< 20 cc	27.5
Bladder	3	0.03cc	33
		<15 cc	16.8
Ureter	3	<0.03 cc	40
Penile bulb	3	< 3cc	25
Femoral heads	3	<10 cc	24
Bile duct	3	< 0.3 cc	36
Renal hilum/vascular trunk	3	<15 cc	19.5
Rib	3	< 0.03 cc	50
		<5 cc	40
Parallel Organ		Volume	Volume Dose (Gy)
Lung (total)	3	<15% lung volume	20
		< 37% lung volume	11
		1500 cc	10.5
		1000 cc	11.4
Total Kidney	3	<200cc	15
Liver	3	<700 cc	17.1

\*NOTE: Avoid circumferential irradiation.

NOTE: For all priority-1 OAR, these are absolute limits, and treatment delivery that exceeds these limits will constitute a major protocol violation.

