**13.2.3 Analysis Plan:**

The main analysis with regards to the primary endpoint is described above, in section 13.2.2. In addition to this Kaplan- Meier curves will be constructed and median PFS times will be calculated for each arm.

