**13.3 Sample Size, Accrual time, and Study Duration****13.3.1 Sample Size**

The chosen design requires 75 events (progressions plus deaths without progressions) and will accrue 96 evaluable patients (48 to each arm) to attain these events. In order to account for patients that: (a) do not have any non-radiated lesions, (b) are deemed ineligible, (c) cancel study participation prior to receiving any randomized treatment, or (d) have a major protocol violation, we will plan to accrue an additional 4 patients making the maximum overall accrual N=100 patients.

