**13.3.3 Primary Endpoint Completion Date for ClinicalTrials.gov Reporting:**

For purpose of ClinicalTrail.gov reporting, the Primary Endpoint Completion Date (PECD) for this study is the time that the 75th event is observed on an evaluable patient. This will be approximately 45 months after the study has begun enrollment under the alternative hypothesis.

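### The only primary PFS analysis excludes randomized patients on post-randomization grounds, one of them undefined, and no all-randomized analysis is planned to check it

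*Combined protocol and SAP*

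**What the plan says.** Section 13.2.1 gives one analysis set for the primary endpoint. Randomized patients who meet the eligibility criteria and who "received any quantity of their randomized care and did not have a major treatment violation will be part of the analysis group".

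Section 13.3.3 places the primary completion date at "the time that the 75th event is observed on an evaluable patient", so the evaluable set also determines when the final analysis falls.

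Section 13.3.1 adds 4 patients to the 96 evaluable ones to cover four kinds of loss: no non-radiated lesion, ineligibility, and those who "c) cancel study participation prior to receiving any randomized treatment, or (d) have a major protocol violation". It expects that the trial "will accrue 96 evaluable patients (48 to each arm) to attain these events".

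Section 13.2.3 adds little: "The main analysis with regards to the primary endpoint is described above, in section 13.2.2", plus Kaplan-Meier curves and medians. Section 13.4.1 names no analysis population for any secondary endpoint. No all-randomized or sensitivity analysis appears anywhere in Section 13.

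The term *major treatment violation* occurs only in 13.2.1. The nearest definition is the note to Table 1.9, on priority-1 organ limits: "treatment delivery that exceeds these limits will constitute a major protocol violation".

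**The concern.** Randomization makes the arms comparable only for the patients as randomized. A set that depends on treatment received, or on violations recorded later, can lose that comparability if exclusions differ between arms and are related to PFS. Here the decision rests on one hazard ratio set against 0.837, and an undefined term helps to decide who enters it. The documents do not say who judges a violation, when, or whether blind to outcome.

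The one event they do call a major protocol violation is a radiation overdose to an organ at risk, which can happen only in Arm 2. If 13.2.1 means that event, the exclusion works in one arm; if it means something else, the text does not say what. Either way, the reader of the result gets no randomized comparison to set beside it.

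**Working it through.** **1. The plan's own design reproduces.** Inputs from Section 13.2.2: medians 9 and 13.5 months, so HR = 9/13.5 = 0.667; looks at 38 and 75 events; limits 1.013 and 0.837; 1:1 allocation.

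With Z = −ln(estimated HR)·√d/2, the mean of Z is −ln(true HR)·√d/2, and the correlation between looks is √(38/75) = 0.712.

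- Limits on the Z scale: −ln(1.013)·√38/2 = −0.040 and −ln(0.837)·√75/2 = 0.770.
- No effect: P(Z₁ > −0.040 and Z₂ > 0.770) = 0.199. The plan states 0.20.
- HR 0.667: the means are 0.405·√38/2 = 1.25 and 0.405·√75/2 = 1.76, and the same probability is 0.802. The plan states 80%.

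The design calculation is sound. The question is which patients it is applied to.

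**2. The two exclusion lists, side by side.**

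| Reason | 13.2.1 | 13.3.1 | Fixed before randomization? |
|---|---|---|---|
| Ineligible | yes | yes | yes |
| No non-radiated lesion | not listed | yes | yes; Section 3.2.2: "Non-irradiated tumor will be identified prior to randomization on the protocol" |
| No randomized treatment received | yes | yes | no |
| Major violation | 'treatment' | 'protocol' | no |

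The allowance for all four reasons together is 100 − 96 = 4 patients.

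**3. What exclusions could do to the error rate.** From the documents: 100 patients, accrual of 3 per month, 9-month median in both arms (no true effect), and both decision rules. Assumptions: 50 per arm, uniform accrual, exponential PFS, and the number and pattern of exclusions, since the documents give no violation rate by arm. There were 40,000 simulated trials per row, with standard error √(0.2·0.8/40,000) = 0.002. A trial is promising if HR ≤ 1.013 at 38 events and HR ≤ 0.837 at 75.

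| Assumed exclusions | P(promising), no true effect |
|---|---|
| None (all randomized) | 0.20 |
| 2 per arm, random or from the shorter-PFS half | 0.20 |
| 4 in Arm 2, random | 0.20 |
| 2, all from the shorter-PFS half of Arm 2 | about 0.25 |
| 4, all from the shorter-PFS half of Arm 2 | about 0.30 |
| 2, all from the shorter-PFS half of Arm 1 | 0.16 |
| 4, all from the shorter-PFS half of Arm 1 | about 0.12 |

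The last four rows are bounding cases. They place half or all of the 4-patient allowance in one arm and one outcome group.

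**4. What the all-randomized set costs in power.** If k of 50 Arm 2 patients get no SBRT effect, take the diluted HR as exp[(1 − k/50)·ln 0.667]. For k = 2 this is 0.678, and for k = 4 it is 0.689. Putting these into step 1 at 38 and 75 events gives power of 0.783 and 0.763, against 0.802 undiluted.

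**5. Are the data there?** For patients who never start treatment, Section 12.3 requires progression and survival data, so they can be analysed.

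**The case against.** The evaluable set is a stated and budgeted choice. Section 13.1 frames the comparison around patients who receive each regimen, and in a phase II screen at one-sided 0.20 an eligible-and-treated set is defensible. The planned losses are few and the evaluable target is balanced at 48 per arm. Two of the four budgeted reasons are baseline facts, so the 0.30 case needs no patient at all to fall under them. A single shorter-PFS exclusion in Arm 2 gives 0.22. One such exclusion plus one random exclusion in each arm gives 0.20.

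Safeguards also make radiation breaches uncommon and documented early. Table 1.7 puts priority-1 limits ahead of target coverage, and Section 15.1.2 has each case reviewed before treatment. Section 7.1.8 wants the radiation record within 21 days of completion. If SBRT starts by day 21 and takes a week (an assumption), that is day 21 + 7 + 21 = 49, before the first scan at about day 1 + 3 × 21 = 64. Any amount of randomized care is enough to stay in the set, so exclusion for non-receipt should be rare.

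All of this stands, and it limits the likely size of any bias. It does not define the violation term, align the two lists, or supply a randomized comparison. An early record also does not fix when a violation is judged.

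A reader might infer that the rule removes Arm 2 patients only and so favours SBRT. The documents do not support that. They never say that 13.2.1 means the Table 1.9 event. Section 7.0 lets a cycle be delayed for major life events "without this being considered a protocol violation", which implies that drug-related violations can occur in either arm. The direction is open as well: Arm 1 exclusions of the same kind lower the rate.

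**Conclusion.** The point holds as a gap in the plan that should be fixed. The primary set uses two post-randomization conditions, one of them undefined and named differently in 13.3.1, and nothing in Section 13 lets the result be checked in all randomized patients.

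A reader might take 0.25 or 0.30 as the trial's real type I error. They are not: they rest on assumed exclusions that are both one-sided and outcome-related, and the documents give no evidence for either. Under balanced or random exclusions the rate stays at 0.20. Nor do the documents show that the evaluable set must lose its role in the decision. Accrual is permanently closed, and Section 13.6.1 sends efficacy reports to the DSMB every six months without saying whether they are by arm. Whether a change of primary set would still precede any sight of comparative data therefore cannot be told from the text. Confidence is medium, because the size of any bias depends on exclusion counts that the documents do not give.

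**What to change.** 1. Before the final comparative analysis, prespecify the primary PFS comparison in all randomized patients by assigned arm, with no exclusion for non-receipt of treatment or for violations, and report it beside the evaluable-set analysis. State in advance which of the two is compared with 0.837 and supplies the 75 events. The all-randomized set is preferable if comparative data have not been seen. Otherwise keep the evaluable set for the decision and report the all-randomized result as a sensitivity analysis. Exclusions that rest only on facts fixed before randomization (ineligibility, no non-radiated lesion) may stay if judged blind to arm and outcome.
2. Use one violation term in 13.2.1 and 13.3.1, defined for both arms and judged blind to outcome. Align the two exclusion lists, and report exclusions by arm and reason.

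The cost is wording in 13.2.1, 13.3.1 and 13.3.3 and a little more analysis work, with no new patients. If the all-randomized set carries the decision, power is about 0.78 or 0.76 instead of 0.80 when 2 or 4 Arm 2 patients get no SBRT effect. Part of that dilution may already be present, because an Arm 2 patient given pembrolizumab without SBRT arguably counts as having received some randomized care.
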